## 1.2. Rationale for the Dose Selection

### 1.2.1. BEM

A 550 mg daily dose of BEM was selected as the optimal dose for evaluation in this study. As described in the BEM Investigator's Brochure, a standard  $E_{max}$  model was used to support this dose selection. As presented in [Figure 1](#), the fitted curve indicates that  $E_{max}$  is achieved with AT-273 (guanosine nucleoside metabolite representing intracellular active triphosphate) area under the plasma concentration-time curve from time 0 to the last time point ( $AUC_{\tau}$ ) greater than 2000 ng/mL\*h. Only the 600 mg/day dose of BEM (553 mg AT-511 free base equivalent) produced AT-273  $AUC_{\tau}$  values that are consistently above the threshold of 2000 ng/mL\*h.

**Figure 1: Exposure-Response Analysis (Study AT-01B-001)**

In addition, as summarized in the BEM Investigator's Brochure, the steady-state exposures of BEM and its metabolites achieved at the no-observed-adverse-effect level doses in the 13-week toxicology studies exceeded the steady-state exposures observed in humans, providing adequate exposure multiples for a daily dose of 550 mg. BEM doses at 550 mg daily have been well tolerated at durations of up to 8-12 weeks.

### 1.2.2. RZR

A daily dose of 180 mg RZR was selected as the optimal dose for evaluation in this study. As described in Section 1.1, prior Phase 2 studies conducted by Merck evaluated both 60 mg and 180 mg daily doses of RZR as part of a 2-drug combination regimen with UPR. CCI [REDACTED]

[REDACTED]

[REDACTED]

[REDACTED]

[REDACTED]

[REDACTED]

At the 180-mg dose of RZR, the target area under the concentration time curve over 24 hours ( $AUC_{0-24h}$ ) is 233  $\mu M \cdot h$ . Based on the animal-to-human  $AUC_{0-24h}$ , the safety exposure multiples in rats at the end of 1 and 6 months of daily dosing, and in dogs at the end of 9 months of daily dosing, were 6-fold and 50-fold respectively, relative to this target. These data support the safety of RZR.

Furthermore, RZR has been generally well-tolerated in HCV-infected patients when administered as once daily doses of 180 mg (282 subjects) for up to 12 weeks combined with UPR alone or at a daily dose of 60 mg (936 subjects) for 8 to 24 weeks in combination with UPR and grazoprevir. There were no observed cardiac or renal safety signals. Drug-related serious

adverse events (SAEs) and drug-related discontinuations due to AEs were rare. There were no consistent treatment-related changes in labs, vital signs, or ECG safety parameter values.

### **1.3. Study Rationale**

A combination of BEM and RZR has the potential to provide a convenient, protease-sparing, pan-genotypic treatment regimen for HCV-infected patients with or without cirrhosis. This Phase 2 study is designed to compare the efficacy and safety of this combination therapy after 8 weeks of treatment. The results of this study will support future later phase studies of BEM and RZR.

### **1.4. Risk/Benefit Assessment**

The non-clinical and clinical data summarized in the respective Investigator's Brochures indicate an encouraging risk-benefit profile for BEM and RZR, supporting advancement of the combination to Phase 2 clinical trials with an expectation of clinical safety and marked anti-HCV efficacy.

Over 750 human subjects have been exposed to BEM across both Coronavirus Disease 2019 (COVID-19) and HCV development programs. There have been no deaths in subjects receiving BEM, and none of the reported SAEs in the BEM program have been related to study drug (ie, investigational medicinal product [IMP]; SAEs have only been reported in the COVID-19 program). Gastrointestinal-related AEs, specifically mild to moderate nausea and vomiting, have been observed more frequently at BEM doses > 550 mg twice daily (reported in the COVID-19 program), however, tolerability at lower doses including the HCV dose of 550 mg daily has been comparable to placebo. In the AT-01B-002 Phase 2 study, BEM was evaluated in combination with a first-generation NS5A inhibitor (daclatasvir) in HCV-infected subjects for durations of up to 8 weeks (9 subjects) and 12 weeks (1 subject) with no safety issues. This study also provided proof-of-concept that a drug combination including BEM (albeit with a less potent NS5A inhibitor) could result in SVR12 with 8 weeks of treatment. There have been no clinically significant patterns in laboratory parameters or ECGs in the BEM program.

Similarly, RZR has been evaluated in over 1800 human subjects, including 1269 HCV-infected subjects where RZR was administered as part of 2 and 3 drug combination regimens (including a nucleoside analog and protease inhibitor). In a prior Phase 2 study in 282 HCV-infected subjects, a daily dose of 180 mg combined with UPR was well tolerated for 12 weeks.

For both compounds, there has been no evidence for genetic toxicity, no concerning findings in developmental and reproductive toxicology studies, and no test-article related findings in safety pharmacology studies. Although there is substantial precedent for drug combinations including nucleoside analogs and NS5A inhibitors for the treatment of HCV, a 13-week combination toxicity study in rats with BEM and RZR has also been conducted, and preliminary results indicate that the combination is well tolerated.

The present protocol mandates thorough clinical and laboratory safety monitoring, with routine testing. Standard serum chemistries, complete blood counts with differentials, urinalyses and clinical AEs will also be monitored. In addition, safety-related stopping rules for individuals (Section 5.6.2) and the study (Section 5.6.3) have been incorporated into the protocol to further reduce subject risk.

Subjects in clinical trials generally cannot expect to receive direct benefit from treatment during participation. However, the potential benefit to subjects is that the combination regimen is reasonably anticipated to be a curative regimen for their HCV infection. The likelihood of rapid HCV RNA clearance to non-detectable levels which can potentially result in SVR achievement is supported by the potent pan-genotypic anti-HCV activity observed in non-clinical virology studies and the clinical studies conducted to date (summarized in Section 1.1). Both compounds have potent pan-genotypic activity and have demonstrated SVR in the clinic in differing combination regimens. For BEM, SVR12 has been observed in HCV-infected subjects after 8 weeks of treatment with a less potent, first-generation NS5A inhibitor (daclatasvir). Furthermore, antiviral activity of BEM after monotherapy was not diminished in GT3-infected subjects or those with compensated cirrhosis, populations which are generally more difficult to treat. Combining BEM with a more potent NS5A inhibitor such a RZR is anticipated to result high rates of SVR12 after 8 weeks of treatment. Therapy with any DAA has the potential to select for the emergence of drug-resistant viral mutants. However, consistent with its high pan-genotypic potency *in vitro*, and its retained activity against prototype nucleoside-resistant mutants, BEM is expected to have a high resistance barrier in HCV-infected patients. RZR retains its potent activity against GT1a RAVs selected by previous NS5A inhibitors in the clinic. Its potency is also not affected by signature RAVs from other HCV DAA classes. The emergence of resistance will be evaluated in this study.

As study AT-01B-004 is designed to explore 8 weeks of treatment, a lead-in group of 60 subjects (non-cirrhotic male and female) will be initially enrolled and treated. Atea will evaluate safety and the rate of sustained virologic response at 4 weeks posttreatment (SVR4) in the lead-in group before enrollment is fully opened. To mitigate the risk of treatment failures, enrollment will only open to the remaining 220 subjects provided that CCI [REDACTED] in the lead-in group experience virologic failure that was not due to poor compliance, and that no study stopping rules are met (Section 5.6.3). Additional protocol-defined virologic stopping rules (Section 5.6.1) are also incorporated to immediately discontinue subjects not responding to treatment. For those subjects who generally comply with the study protocol and experience lack of efficacy (failure to achieve SVR12 or sustained virologic response at 24 weeks posttreatment [SVR24]) with the investigational regimen, the Sponsor may reimburse the investigator for the cost of a course of post-study medication depending on local drug access and reimbursement policies.

These considerations support a favorable risk/benefit profile for evaluation of BEM and RZR in this study.

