### **5.6. Stopping Rules**

#### **5.6.1. Individual Virologic Stopping Rules**

Treatment will be discontinued in any subject with on-treatment virologic failure, defined as any one of the following:

- Confirmed  $1 \log_{10}$  increase in HCV RNA from post-baseline nadir
- Confirmed increase in HCV RNA  $\geq$  LLOQ in any subject who achieved HCV RNA  $<$  LLOQ

Confirmation should be performed as soon as possible after an initial HCV RNA value that may indicate virologic failure is reported.

After completion of study-related procedures in the current study, the investigator may offer an approved poststudy HCV treatment regimen consistent with local standard-of-care treatment guidelines to subjects who have on-treatment virologic failure or posttreatment virologic relapse. For those subjects who generally comply with the study protocol and experience lack of efficacy (failure to achieve SVR12 or SVR24) with the investigational regimen, the Sponsor may reimburse the investigator for the cost of a course of poststudy medication depending on local drug access and reimbursement policies.

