## 5.7. Premature Discontinuation

Subjects may voluntarily discontinue treatment or withdraw from the study at any time. They may also be removed from the study at the discretion of the investigator or Sponsor at any time. The investigator may withdraw a subject at any time if it is determined that continuing the study would result in a significant safety risk to the subject.

Premature treatment discontinuation may occur for any of the following reasons:

- Noncompliance with the protocol requirements
- Pregnancy
- On-treatment virologic failure, as defined in Section 5.6.1
- Adverse event precluding further study participation due to safety concerns or compliance issues
- Subject request
- Investigator request
- Sponsor request

Subjects who prematurely discontinue treatment should have an Early Termination (ET) visit and be asked to return for the scheduled post-treatment follow-up visits.

In subjects who require additional care after their participation in the trial has ended or been completed, such as that necessary to monitor an AE(s), continued follow-up and care will be

provided until resolution of the AE(s). For those who experience a lack of efficacy and virologic failure, refer to Section [5.6.1](#) for additional reimbursable treatment/care.

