#### **8.7.2.1. On-Treatment Virologic Failure**

On-treatment virologic failure is defined as any of the following, while on-treatment:

- Not achieving  $\text{HCV RNA} < \text{LLOQ}$
- Confirmed 1  $\log_{10}$  increase in HCV RNA from post-baseline nadir (would call this “virologic rebound” if we want to name it in parenthesis)
- Confirmed increase in  $\text{HCV RNA} \geq \text{LLOQ}$  in any subject who achieved  $\text{HCV RNA} < \text{LLOQ}$

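### Protocol 1.4 says the Section 5.6.1 rules stop non-responders at once, but 5.6.1 acts only on a confirmed rise in HCV RNA

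*Protocol*

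**What the plan says.** **Protocol 1.4 (Risk/Benefit Assessment)** lists the safeguards for an exploratory 8-week regimen. After the lead-in gate it adds: "Additional protocol-defined virologic stopping rules (Section 5.6.1) are also incorporated to immediately discontinue subjects not responding to treatment". The section then concludes that risk/benefit is favourable.

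**Protocol 5.6.1 (Individual Virologic Stopping Rules)** is the operative text: "Treatment will be discontinued in any subject with on-treatment virologic failure, defined as any one of the following". Two items follow:

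- a confirmed 1 log10 "increase in HCV RNA from post-baseline nadir";
- a confirmed rise to LLOQ or above "in any subject who achieved HCV RNA" below LLOQ.

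It also asks for a repeat test: "Confirmation should be performed as soon as possible after an initial HCV RNA value that may indicate virologic failure is reported".

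**Protocol 5.7 (Premature Discontinuation)** gives one virologic reason for stopping treatment, "On-treatment virologic failure, as defined in Section 5.6.1". The other reasons are noncompliance, pregnancy, adverse event, and subject, investigator or Sponsor request. Of subjects generally it says: "They may also be removed from the study at the discretion of the investigator or Sponsor at any time".

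**SAP 8.7.2.1** opens with "On-treatment virologic failure is defined as any of the following, while on-treatment" and lists three items: the two from Protocol 5.6.1, plus never reaching HCV RNA below LLOQ. **SAP 8.8**, which covers the secondary endpoints, defines virologic failure by the two rise-based items only.

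**The concern.** Section 1.4 tells ethics committees and investigators that a protocol-defined rule removes non-responders. The rule it cites is written for rebound and breakthrough. Section 1.4 also acknowledges that any direct-acting antiviral can select resistant virus, so continued dosing without response is a risk this sentence would be expected to cover.

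There is a linked analysis question. If the same subject is an on-treatment virologic failure in one SAP section and not in another, the secondary failure rate and the lead-in decision depend on which section the programmer follows.

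**Working it through.** No sample-size or power figure is involved. The check applies the two 5.6.1 criteria to possible HCV RNA courses and then compares the definitions.

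**Inputs**

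- Criteria: Protocol 5.6.1 and SAP 8.7.2.1, as above.
- On-treatment HCV RNA at Weeks 1, 2, 4, 6 and 8 (Protocol Table 2).
- Assumption: confirmed means two consecutive qualifying values.
- Assumption: LLOQ of 10, 15, 25 or 50 IU/mL, that is log10 values from 1.00 to 1.70. The documents give no LLOQ.
- The courses are illustrative and are not data from the documents.

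**Step 1. Apply the rules.** Criterion 1 is met if (value − lowest earlier post-baseline value) ≥ 1 log10 on two consecutive tests. Criterion 2 is met if a value below LLOQ is followed by two consecutive values at or above LLOQ.

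| Course (log10 IU/mL at Weeks 1, 2, 4, 6, 8) | Largest rise from nadir | 5.6.1 met? | Never < LLOQ (SAP 8.7.2.1)? |
|---|---|---|---|
| Flat: 6.0 throughout | 0 | No | Yes |
| Small fluctuation: 6.1, 5.8, 6.2, 5.9, 6.1 | 6.2 − 5.8 = 0.4 | No | Yes |
| Plateau: 4.5, 3.8, 3.5, 3.5, 3.5 | 0 | No | Yes |
| Slow fall: 5.5, 5.0, 4.5, 4.0, 3.5 | 0 | No | Yes |
| Never suppressed, later rise: 5.2, 5.0, 6.1, 6.2, 6.1 | 6.2 − 5.0 = 1.2 | Yes, criterion 1 | Yes |
| Rebound: 4.0, 2.5, 4.0, 5.0, 5.5 | 5.5 − 2.5 = 3.0 | Yes, criterion 1 | Yes |
| Breakthrough: 2.0, 0.5, 0.5, 2.0, 3.0 | 3.0 − 0.5 = 2.5 | Yes, both | No |

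The result is the same at all four assumed LLOQ values. The first four courses are the gap: no fall, or an incomplete fall, without a confirmed 1 log10 rise.

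**Step 2. Look for another rule that closes the gap.** The virologic reason in 5.7 points back to 5.6.1. What remains for lack of response is investigator or Sponsor request, which is discretionary and not the rule that 1.4 cites.

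**Step 3. Follow such a subject through the SAP.** SAP 8.7.2.2 defines relapse only for subjects below LLOQ when treatment stops, so this subject is not a relapse. Under 8.7.2.1 the subject is an on-treatment failure; under 8.8 the subject is not a virologic failure at all.

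- *SVR12, treatment completed:* SAP Table 5 uses the post-treatment result, so this classification does not alter SVR12.
- *SVR12, stopped early at discretion without meeting 5.6.1:* Table 5 scores an early stop for virologic failure as a failure, but excludes subjects in its residual row. The table does not say which definition of virologic failure applies.
- *Lead-in rule:* SAP 5.1 closes enrolment above 10%, given as more than 6 subjects. 6/60 = 10.0% does not exceed the limit; 7/60 = 11.7% does. At that boundary one classification decides the outcome.

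**The case against.** Section 1.4 is narrative and defers to 5.6.1, which is clear. Sites act on 5.6.1, HCV RNA is measured at every treatment visit, the study is unblinded, and 5.7 allows removal at discretion. An analysis definition may also legitimately differ from a stopping rule. All of this stands. It limits the consequence, but it does not make the 1.4 statement true of the rule it cites.

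The documents do not support several stronger readings that a reader might infer:

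- *No never-suppressed subject can meet a virologic stopping rule, because both criteria need a prior fall.* Criterion 1 is measured from the lowest post-baseline value, which need not lie below baseline. A never-suppressed subject with a confirmed 1 log10 rise meets it.
- *Such subjects must continue to Week 8.* They may be stopped at discretion under 5.7. The full 56 doses is a ceiling.
- *About 30% of subjects could be affected.* Protocol 1.1 reports that 70% of 10 subjects on a different combination were below LLOQ by Week 2, so 3 were not. In that study 8 of 9 plus 1 of 1, that is 9 of 10, reached SVR12. At least 2 of those 3 therefore reached SVR12: they were slower responders, not non-responders.
- *The SAP criterion shows that dosing should have been stopped.* The 8.7.2.1 item has no time point, and 8.7.2.2 treats the Week 8 value as on-treatment after 51 or more days. It can be judged only when treatment ends, so it classifies an outcome and could not act as a stopping rule.
- *The favourable risk/benefit conclusion falls.* It also rests on prior safety and activity data, the lead-in gate and the safety stopping rules.

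**Conclusion.** The mismatch is real but narrow. Section 1.4 claims a protection that 5.6.1 does not give to a subject whose HCV RNA is flat, plateaued or slowly falling, stays at or above LLOQ, and shows no confirmed 1 log10 rise. Discretion under 5.7 is then the only route to stopping for lack of response. The word for immediate action in 1.4 also sits uneasily with the confirmation step in 5.6.1, though that is minor.

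Probably few subjects are affected. Protocol 1.1 reports mean maximum falls of 4.4 to 4.6 log10 after 7 days of BEM alone and falls above 3 log10 with 5 days of RZR alone, but it gives no rate of true non-response, so no number can be put on it. The finding rests on the text; the assumed LLOQ range and the two-test reading of confirmation serve only the illustration.

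The difference between SAP 8.7.2.1 and 8.8 is a separate defect. It can change the secondary virologic failure count and, at the boundary, the lead-in decision.

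**What to change.** 1. **Protocol.** Reconcile Sections 1.4 and 5.6.1 so that the stated safeguard matches the operative rule. Which text changes is for the clinical team. Section 5.7 already refers to 5.6.1 and will follow.
2. **SAP.** Use one analysis definition of on-treatment virologic failure in 8.7.2.1 and 8.8. State that it feeds the secondary endpoint and the lead-in rule in 5.1, and say whether it also governs the early-discontinuation row of Table 5.
3. **Link between the two.** The analysis definition need not equal the treatment-stopping rule. If it differs from Protocol 5.6.1, say so in one sentence of the SAP.

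The cost is amendment wording in the protocol and a short SAP edit before database lock. HCV RNA is already collected at every treatment visit, so no new scheduled visits or samples are needed.

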## **2. STUDY OBJECTIVES**

### **2.1. Primary Objectives**

The primary objectives of this study are:

- To evaluate the safety and tolerability of BEM + RZR
- To evaluate the efficacy of BEM + RZR as assessed by the proportion of subjects achieving SVR12

### **2.2. Secondary Objectives**

The secondary objectives of this study are:

- To evaluate the efficacy of BEM + RZR, as assessed by the proportion of subjects experiencing virologic failure (either on-treatment or post-treatment relapse [by 12 weeks post-treatment])
- To evaluate the efficacy of BEM + RZR as assessed by the proportion of subjects achieving SVR24

### **2.3. Exploratory Objectives**

- To evaluate the effect of baseline RAVs in NS5A and/or NS5B on the efficacy of BEM + RZR
- To evaluate the emergence of NS5A and NS5B RAVs in subjects who experience virologic failure
- To evaluate antiviral activity/viral kinetics (VK) of BEM + RZR
- To evaluate the PK and VK of BEM + RZR in the subgroup of subjects who agree to additional serial PK and VK sampling

[figure not shown]
### 3. STUDY DESIGN

#### 3.1. General Study Design

This is an open-label trial to evaluate 8 weeks of treatment with BEM + RZR in subjects with chronic HCV infection (Figure 2). Approximately 280 treatment-naïve subjects with genotype (GT) 1, 2, 3, 4, 5, 6, or 7, either without cirrhosis or with compensated cirrhosis, will be enrolled.

A lead-in group of 60 non-cirrhotic subjects will initially be enrolled. At 4 weeks posttreatment, this lead-in group will be evaluated for safety, SVR4, and virologic relapse; enrollment will open to the remaining 220 subjects provided that **CCI** [REDACTED] in the lead-in group experience virologic failure that was not due to poor compliance and no study stopping rules are met (Section 5.6.3).

**Figure 2:** Study Design

a Can be extended to 6 weeks under extenuating circumstances with Sponsor approval.  
BEM = bemnifosbuvir; RZR = ruzasvir; SVR4 = sustained virologic response at 4 weeks posttreatment

Subjects will be screened for up to 4 weeks, although this can be extended for up to 6 weeks for extenuating circumstances with Sponsor approval. Such circumstances may include awaiting reporting of laboratory results or scheduling assessment of cirrhosis (eg, FibroScan®) if needed. Re-screens may be approved on a case-by-case basis by the Sponsor (re-screened subjects will be assigned a new subject number).

At the end of the screening period (Baseline; Day 1), eligible subjects will enter the treatment period and receive BEM + RZR for 8 weeks. After Day 1 during the treatment period, subjects

may self-administer study drugs (ie, IMP) at home, with the exception of subjects who agree to additional PK and/or PK-VK blood sampling as part of up to two substudies. These subjects will be required to take their study drug in the clinic on certain days (see [Table 3](#)).

Subjects will return to the clinic for evaluations at Weeks 1, 2, 4, 6, and 8 (End of Treatment [EOT]) during the treatment period.

Following their last visit of the treatment period (including subjects who prematurely discontinue treatment) subjects will enter the Follow-up period and return to the clinic for evaluations at Follow-up Weeks 4, 12, and 24. End-of-Study (EOS) is defined as the visit at 24 weeks posttreatment.

Adverse events and concomitant medications will be reviewed during visits throughout the treatment and follow-up periods. Subjects may also be contacted between visits to assess their compliance with the dosing regimen (during the treatment period) and to discuss AEs and concomitant medications.

The primary endpoint is SVR12. Secondary endpoints include virologic failure and SVR24. Exploratory endpoints are resistance to either study drug (BEM or RZR), SVR12 in subgroups defined by demographics and/or baseline characteristics, HCV RNA changes from baseline and exposure-response relationships. Safety endpoints are the incidence of AEs, SAEs, and AEs resulting in treatment discontinuation; clinical laboratory abnormalities; vital sign measurements; and ECG parameters.

At clinical sites that agree to participate, there will be two optional substudies (PK only; PK-VK), each requiring separate consent; up to 100 subjects can consent to either or both. Subjects who consent to the PK-only substudy will provide additional blood samples at any planned treatment visit as early as Week 2 based on convenience for subject and investigator. Subjects who consent to the PK-VK substudy will provide additional blood samples a) on Day 1; and b) on Days 2 and 3 (24 and 48 hours after the first dose;  $\pm$  2 hours). Study drug will be administered at the clinic on these days (see [Table 3](#)).

Patients with HCV or HCV patient groups were not consulted. The study conforms to many aspects of canonical HCV study design and patient care, as described in both health authority guidance  and clinical practice guidelines .

This is a global clinical trial that complies with the European Union Clinical Trial Regulations. Results will be released to a publicly accessible web site (eg, Clinical Trial Information System [CTIS]) after the last European subject's completion of the study. However, if the study is ongoing outside the EU as of that date, results will be released after the last subject's completion date.

